Official Study Title: Investigation of the Effect of Elastic Lower Extremity Orthosis on Gait and Balance Parameters in Children With Spastic Cerebral Palsy: A Randomized Controlled Trial

ClinicalTrials.gov Identifier: NCT07122362

Document Date: April 19, 2025

Study Brief Title: Effect of Elastic Lower Extremity Orthosis on Gait and Balance Parameters in Children with Spastic Cerebral Palsy

Study Period: Start: August 25 2025– End: November 01 2025

1. Study Objective

The primary objective of this study is to determine the effect of an elastic lower extremity orthosis, applied in addition to conventional neurodevelopmental treatment, on gait and balance parameters in children with spastic cerebral palsy presenting with an in-toeing gait pattern.

2. Study Design

Single-blind randomized controlled trial

Biostatistician will be blinded to group allocation

Groups will be assigned using simple randomization

3. Study Population

Inclusion Criteria

Voluntary participation

Diagnosis of spastic cerebral palsy

GMFCS level 1–3

Age 18–84 months

Written and verbal informed consent from parents

Exclusion Criteria

GMFCS level 4–5

Botulinum toxin injection or surgery to lower extremities/pelvis in the past 6 months

Sample Size

Each group: 13 participants

Total: 26 participants

Calculated using G*Power with 95% power and $\alpha = 0.05$

4. Intervention

Neoprene elastic lower extremity orthosis

7 days per week, 6–8 hours per day, 8 weeks

In addition to conventional neurodevelopmental therapy

5. Data Collection and Measurements

Demographics: age, sex, height, weight, CP type, GMFCS level

Gait: Edinburgh Visual Gait Analysis (17 parameters)

Balance: Pediatric Balance Scale (14 items, 0–4 points)

Measurements at baseline and after 8 weeks

Video recordings obtained

No personal identifying information included

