## **Statistical Analysis Plan (SAP)**

Analyses will be performed using IBM SPSS Statistics 26.0

Normality assessment: histograms, probability plots, Shapiro–Wilk test, skewness/kurtosis, coefficient of variation

Descriptive statistics: nominal/ordinal → frequencies and percentages, numerical → median ± percentiles or mean ± SD

Categorical variables: Chi-square (Pearson or Fisher)

Within-group comparisons (pre/post): Paired t-test / Wilcoxon

Between-group comparisons: Student t-test / Mann–Whitney U

Significance level:  $p < 0.05$

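### The objective is to determine the orthosis effect, but the SAP prespecifies no between-arm estimate or confidence interval, so a non-significant result from 26 children could be misread as no effect

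*SAP*

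**What the plan says.** The Protocol (section 1) states: "The primary objective of this study is to determine the effect of an elastic lower extremity orthosis", given on top of conventional neurodevelopmental treatment, on gait and balance. Under Sample Size it gives "Each group: 13 participants" and "Total: 26 participants", with the basis "Calculated using G*Power with 95% power" and α = 0.05. No effect size, SD, sidedness or test is given. Section 2 adds "Groups will be assigned using simple randomization". Section 5 lists a gait instrument with 17 parameters and the Pediatric Balance Scale, both measured at baseline and after 8 weeks.

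The SAP is a short list that runs from software to significance level. The lines that bear on this point are:

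- "Descriptive statistics: nominal/ordinal → frequencies and percentages, numerical → median ± percentiles or mean ± SD"
- "Within-group comparisons (pre/post): Paired t-test / Wilcoxon"
- "Between-group comparisons: Student t-test / Mann–Whitney U"
- a significance threshold of p < 0.05.

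No line names a between-arm difference, an effect size or a confidence interval. No line says whether the arms are compared on the 8-week value or on change, or how a non-significant result will be worded.

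**The concern.** An objective about the size of an effect calls for an estimate with a statement of its precision. The SAP commits only to summaries of each variable and to p-values. In a trial this small the gap matters in both directions. A p-value above 0.05 cannot tell no effect from a large effect measured imprecisely. A p-value below 0.05 says nothing about how large or small the effect might be. At stake is whether the report can state which orthosis effects the data are compatible with, or only whether a threshold was crossed.

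**Working it through.** **Inputs.** From the Protocol: 13 per arm, 26 in total, α = 0.05, 95% power. Assumed, because the documents do not say: two-sided testing, exactly 13 v 13, a common SD and no dropout. Differences are in units of the SD of whatever quantity is compared. The observed differences below are illustrations, not forecasts.

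**1. The plan's own figure.** The 13 per arm cannot be reproduced forwards, since no effect size is stated. Solved backwards with the noncentral t distribution, 95% power at 13 per arm needs a standardized difference of 1.47 (two-sided) or 1.33 (one-sided). For a two-sided Mann–Whitney test, with efficiency 3/π, it needs about 1.51. If the calculation was for a paired within-arm test, the standardized mean change would be 1.09 (two-sided) or 0.97 (one-sided), and the 95% would not describe the between-arm comparison at all.

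**2. Precision of a between-arm difference.**

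Half-width = t(0.975, 24) × √(2/13) = 2.064 × 0.392 = 0.81 SD; full width 1.62 SD.

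**3. What a p-value alone would leave unsaid.** With test statistic t = d / 0.392 on 24 df:

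| Observed difference d (SD) | p | 95% CI (SD) |
|---|---|---|
| 0.3 | 0.452 | −0.51 to 1.11 |
| 0.5 | 0.215 | −0.31 to 1.31 |
| 0.7 | 0.087 | −0.11 to 1.51 |
| 0.8 | 0.053 | −0.01 to 1.61 |

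All four miss p < 0.05, and none excludes an effect above 1 SD.

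**4. How often this could arise.** Two-sided t-test power at 13 per arm is 23% for a true difference of 0.5 SD, 50% for 0.8 SD and 69% for 1.0 SD. The chance of a non-significant result is therefore 77%, 50% and 31%.

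**5. Sensitivity to the assumptions.**

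- Dropout: with 12, 11 or 10 per arm the half-width is 0.85, 0.89 or 0.94 SD.
- Unequal arms: simple randomization need not give 13 v 13. At 10 v 16 the half-width is 2.064 × √(1/10 + 1/16) = 0.83 SD, so this effect is small.
- Baseline adjustment: half-width = t(0.975, 23) × √((2/13)(1 − r²)), in SDs of the 8-week score. This is 0.70, 0.58 or 0.49 SD if the pre/post correlation r is 0.5, 0.7 or 0.8 (assumed).

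**6. What can be recovered from the planned summaries.** If the t-test is used, arm means, SDs and numbers give a crude difference and interval for whichever quantity is summarised. An interval for a difference in change needs the SD of change, and the SAP does not say that this will be reported. If Mann–Whitney is used, the Hodges–Lehmann shift is the median of all 13 × 13 = 169 between-arm pairwise differences. It needs individual values, and medians with percentiles do not supply them.

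**The case against.** The strongest reply has four parts.

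- **The objective is worded in the usual way and binds the plan to no particular output.** This stands in part. The two documents do not contradict each other, and the tests are valid without an interval. The point is an omission.
- **Descriptives are planned, so the trial returns more than a yes/no answer.** This also stands in part. A reader might infer that the SAP delivers nothing but a verdict. That is too strong, because arm means and SDs allow a crude difference if the t-test is used. The reply fails if Mann–Whitney is used, and in neither case is a contrast chosen in advance.
- **The trial has 95% power.** This does not answer the point. The effect behind that figure is not given. For a two-group t-test it would have to be about 1.3 to 1.5 SD, so the claim offers little protection at 0.5 to 1.0 SD.
- **An interval does not show whether a gain is worthwhile.** This is correct as far as it goes. Neither document gives a minimal important difference on either scale, so the interval shows only which effects are compatible with the data. That is still more than the p-value shows.

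A reader might also infer that a null result will be reported as absence of effect. Neither document says how one will be interpreted, so the supportable statement is that it could be misread that way.

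**Conclusion.** The concern holds as an omission. The plan sets out to determine an effect but prespecifies only tests and summaries of each variable, with no between-arm estimate or interval. Under 13 v 13, a common SD and no dropout, the missing interval has a half-width of 0.81 SD, and an observed difference of that size is the smallest that reaches p < 0.05. Non-significant results in a wide band below it would still leave effects above 1 SD open. Dropout or unequal arms widen the interval; baseline adjustment may narrow it appreciably, depending on a correlation that the documents do not give.

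This should be changed, but it does not invalidate the trial. It also depends on a prior decision: an interval can be specified only once the SAP says which contrast and which gait quantity are meant.

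**What to change.** Add to the SAP:

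> For the gait score (one summary across the 17 parameters, named in advance) and the Pediatric Balance Scale total, the main result is the orthosis-minus-control difference at 8 weeks, adjusted for the baseline value (or, if not adjusted, the difference in change from baseline), in scale points with a two-sided 95% CI. If the Mann–Whitney test is used, it is applied to change from baseline, and the Hodges–Lehmann shift with its 95% CI is reported. p ≥ 0.05 will not be described as no effect; the conclusion will state the range of effects in the interval.

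The sponsor should settle the adjusted or change option, and preferably the choice between t-test and Mann–Whitney, before looking at outcome data. Otherwise the reported quantity still depends on the data.

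The cost is one more standard output per outcome and a decision on the gait summary. No new data are needed and the sample size does not change. Reporting the interval does not in itself make the trial more precise; it makes the imprecision visible.
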